## Abstract

The rising prevalence of chronic illnesses threatens the sustainability of the healthcare system, especially due to the high cost of frequent hospitalizations. Effective self-management of chronic disease can reduce the need for urgent care but helping patients to master complex decision-making and to implement lifestyle changes is difficult. Telemonitoring systems are a promising adjunct in this regard. Such systems allow patients to monitor their physiological state (e.g. weight, blood pressure) and to receive both automated and real-time feedback from health care providers. Current systems tend to be inconvenient and costly to implement in existing clinical settings and are often limited to the monitoring of one chronic condition. We believe that delivering telemonitoring through a mobile phone will enable patients with complex chronic conditions to track their health, receive automated feedback relevant to their unique situations, and improve communication with their health care team in a cost effective and intuitive way.

In order to test the effectiveness of the intervention, we propose a 6-month randomized controlled trial of 146 patients. The study will include patients with a diagnosis of any of the following conditions or combinations of these conditions: heart failure, chronic obstructive pulmonary disease, chronic kidney disease, and/or uncontrolled hypertension. Insulin-requiring diabetes will be included as a co-morbidity to be supported by the telemonitoring application if the patient also has at least one of the four above chronic conditions. Patients will be assigned to either (1) the control group receiving usual care, or (2) the group using the mobile telemonitoring system in addition to usual care. We hypothesize that our mobile intervention will be a cost-effective and scalable tool that will improve health outcomes and quality of care, while empowering and reassuring patients and their family.

## **Background**

Patients with chronic illnesses, including those with multiple chronic conditions (MCCs), face numerous challenges in the self-management of their conditions, particularly complex decision-making, varying and often contradictory clinical management advice, and frequent hospitalizations. A 2011 Canadian Institute for Health Information study found that three out of four Canadians age 65 and older reported having at least one chronic condition, while one in four seniors reported having three or more (1). While 75% of health care dollars are solely devoted to managing chronic illnesses, 5% of the population **consumes > 50% of all dollars devoted to healthcare** (2). With the increasing prevalence of chronic illnesses and MCCs (1), the sustainability of our healthcare system is threatened. However, through enhanced patient self-care and clinical management, significant reductions in healthcare spending and improved health outcomes could be achieved.

eHealth tools may empower patients and their informal caregivers in more effective self-management of MCCs, and serve as a critical decision-support tool for their healthcare providers (HCP). In particular, telemonitoring enables patients to track their vital signs and symptoms, and also to receive automated instruction and clinical intervention during “teachable moments” (i.e., clear actions are provided when the context is most appropriate). The automated instructions can be based on current physiological measurements, self-monitored symptoms, and readily analyzed trends in both (3). Automated real-time alerts and frequently collected and analyzed physiological data can also support clinical decisions by healthcare providers (3).

A growing body of research on telemonitoring interventions for single chronic conditions exists, but it focuses on singular conditions such as diabetes, hypertension, or heart failure (4-6). Several studies and systematic reviews have shown that the use of telemonitoring interventions for the management of chronic conditions (e.g., heart failure, hypertension and diabetes) lead to positive health outcomes and significant reductions in healthcare costs (7-11). Contradictory studies that did not find improvements often excluded a self-care component, were difficult to use, or did not target patients who were the most ill and frequently hospitalized (12-15). Due to the added complexity involved, very few studies have focused on the use of telemonitoring amongst high-risk patients with MCC, even though these patients may benefit the most from such an intervention (16-21).

Based on our existing telemonitoring tools and extensive experience in evaluating such technologies focused on patients with chronic conditions, we propose conducting an investigation of the use of mobile phone-based telemonitoring for the self-management of complex patients. The rationale for the use of mobile phones is that it enables a cost-effective data hub that allows

patients to transmit physiological and symptom information from any location with cell phone reception.

For our project, complex patients will be defined as those who are at high-risk for hospitalization, exacerbations, and disease progression, as well as patients with multiple chronic conditions. In particular, heart failure (HF) and chronic obstructive pulmonary disease (COPD) are among the most common causes of avoidable hospitalizations (22), and CKD patients incur very high costs when hemodialysis is required (23, 24). Thus, delaying the need for hemodialysis through eHealth tools would improve patient quality of life and defer substantial health service utilization. In addition, improving self-care of patients prior to requiring hemodialysis may result in patients later opting for more independent interventions, such as home hemodialysis.

## **Objectives**

The objective of the randomized controlled trial (RCT) is to evaluate a mobile phone-based telemonitoring system for management of a variety of chronic conditions, including HF, COPD, CKD, insulin-requiring diabetes and uncontrolled hypertension in specialty clinic settings. The RCT will be registered into clinicaltrials.gov and ISRCTN.org prior to commencement.

The telemonitoring system, named “*Medly*”, has been developed through leveraging technology and accumulated expertise in the development and clinical trials of mobile telemonitoring systems in the areas of hypertension, diabetes, asthma, heart failure (HF), chronic obstructive pulmonary disease (COPD), and chronic kidney disease (CKD) (3, 4, 25-32). The development and usability testing of *Medly* for this RCT was completed under the University Health Network research ethics board approval number 13-7085-BE. Research ethics board approval numbers for trials using this telemonitoring platform that have been conducted at the University Health Network include 08-0192-BE (HF RCT), 14-7638 (CKD pilot), and 14-7756-AE (COPD pilot).

**Central Research Question:** What is the impact of a telemonitoring system for patients with complex chronic illnesses on health status, cost, self-management, clinical management, health outcomes, and health service utilization?

## **Patient Population**

### ***Inclusion Criteria***

Patients who meet the following criteria will be considered for inclusion in the study:

- Adults (age 18 years or older)
- Diagnosed with HF, COPD, CKD, insulin-requiring diabetes and/or uncontrolled hypertension
- Followed by at least one of the following physicians:
  - Followed by a cardiologist at the Heart Function Clinic, University Health Network, who has primary responsibility for management of the patient's HF
  - Followed by a respirologist at the Asthma and Airway Centre, University Health Network, who has primary responsibility for management of the patient's COPD
  - Followed by [name] or another hypertension specialist at the Mount Sinai Hospital, who has primary responsibility for management of the patient's CKD and/or hypertension
  - Followed by an endocrinologist at the Endocrinology Clinic at UHN, such as [name].
- Patients with HF as the primary chronic disease:
  - Patients with HF with reduced ejection fraction (EF<0.40)
- Patients with COPD as the primary chronic disease:
  - Spirometrically confirmed diagnosis of COPD of GOLD Stage II or higher (defined as post-bronchodilator FEV1 < 80% predicted and FEV1/FVC ratio < 70%) and,
  - smoking history of  $\geq$  20 pack-years or homozygous alpha-1 antitrypsin deficiency and,
  - Prescribed an action plan for the early self-treatment of acute exacerbations
- Patients with CKD as the primary chronic disease:
  - Grade 3-5 (eGFR < 60mL/1.73 m^2)
- Patients with uncontrolled hypertension as the primary chronic disease:
  - For non-diabetics: blood pressure  $\geq$ =140/90 mmHg auscultatory (manual measurement) or  $\geq$ =135/85 mmHg oscillometric (automated measurement)
  - For diabetics: blood pressure  $\geq$ =130/80 mmHg
- Patient or their caregiver speaks and reads English adequately to provide informed consent and understand the text prompts in the application.
- Ability to comply with using the telemonitoring system (e.g, able to stand on the weight scale, able to answer symptom questions, etc.).

### ***Exclusion Criteria***

Patients will be excluded from participating in the pilot study for any of the following reasons:

- Patients on mechanical circulatory support
- Patients on the heart transplant list
- Terminal diagnosis with life expectancy < 1 year
- Dementia or uncontrolled psychiatric illness
- Resident of a long term care facility

### **Patient Recruitment**

Patients will be recruited during regularly scheduled visits to the UHN and Mount Sinai Hospital clinics associated with their chronic illnesses. After the clinician determines that the patient is eligible for recruitment, he/she will ask the patient if they are willing to speak to the study coordinator regarding the study. All eligible participants, based on the inclusion/exclusion criteria above, will be asked to sign a written consent form prior to being enrolled in the study (Appendix 1).

An additional recruitment strategy to asking patients if they are interested in participating in the study during their regularly scheduled clinic visit may be employed to speed up patient enrolment. This recruitment strategy has previously been used with great success for a completed and a current study at the University Health Network by [name] (co-investigator) at the Renal Clinic. It involves identifying interested patients prior to their clinic visit. The research study coordinator, an independent third party who is not part of the clinical care team, will generate an eligible patient mail out list. This list will be derived from the general clinic roster at the Hypertension Clinic (Mount Sinai Hospital) and at the Heart Function Clinic (UHN); the list will be screened and verified by the clinic nurses/physicians to ensure appropriateness (as determined by the study inclusion criteria) for mailing out invitations about the study. A separate REB amendment will be sent to the Mount Sinai Hospital REB. The mail out study invitation will be used in order to determine interest of patients who are not scheduled for an upcoming clinic visit at UHN. After identifying eligible patients, the research coordinator will mail out an invitation letter including a study description and consent form along with a pre-addressed and stamped envelope to return the signed consent form to the clinic (see Appendix 2). This will be mailed only to potential participants who have been reviewed by the clinic staff as “appropriate to be approached”. The letter will be mailed to the potential participants on behalf [name] for the Hypertension Clinic patients at Mount Sinai Hospital and [name] for the Heart Function Clinic patients at the University Health Network. Each will sign the letter as they are the clinician leads in the respective clinics. The patients will also be provided with the

coordinator's phone number in case they require additional information or want to discuss aspects of the study, as well as to indicate interest in the study. For those who did not respond to the letter within two weeks of mailing, the study coordinator will contact them over the phone to explain the study and determine interest in participating. For all those interested in participating, the study coordinator will arrange a date and time to meet in the clinic. Details of the study and the consent form will be reviewed in-person at this time to ensure that patients are fully informed about all aspects of the study and are freely providing their consent to participate.

To perform a sample size calculation, the primary outcome measure SF-36 was used. Assuming a moderate effect size on the general health dimension of the SF-36 of 10.5 points (39), a score of 57 +/- 21 for the control group (40), 80% power, and alpha=0.05 (two-sided), the sample size per group was calculated to be 63 (<http://clincalc.com/Stats/SampleSize.aspx>). Assuming 15% of patients will be lost to follow-up (including mortality) (36, 37), the sample size per group is 73. Hence 146 patients will be enrolled during the trial and randomized 1:1 into control and telemonitoring groups.

To perform the randomization, the online computer generated randomization tool, Research Randomizer, will be used ([www.randomizer.org](http://www.randomizer.org)). The study coordinator performing the recruitment will be blinded until the patient has consented to participate. The participants will be blocked randomized (blocks of 4) and stratified into groups according to their primary condition (HF, COPD, hypertension, insulin-requiring diabetes, and CKD). The HF group will further be stratified based on NYHA classification (NYHA class 2-3, NYHA class 4), and the hypertensive patients will be stratified to those with and those without diabetes.

A member of the clinical care team (e.g., physician or nurse) will briefly introduce the study to the patient and ask if the patient would be willing to meet with the study coordinator. If the patient agrees, the study coordinator will meet with the patient to discuss the study in more detail. If the patient is interested in participating in the study, the coordinator will evaluate the patient for inclusion/exclusion criteria and obtain written consent for participation. Once this is completed, the study coordinator will provide the patient and, if appropriate, his/her caregiver with training on the telemonitoring system.

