  - symptoms score from the telemonitoring system
  - blood pressure as measured by an automatic blood pressure monitor
- Hypertension
  - blood pressure as measured by an automatic blood pressure monitor
  - average 7-day blood pressure
- Diabetes
  - HgbA1c

**Data Acquisition:** Number of hospitalizations, days in hospital, number of ED and clinic visits, and medications will be determined through the hospital EMR and a manual chart review of all participants' clinical records. Combined hospitalization will be verified by patient participants through self-report with the help of a questionnaire. The cost of the intervention will be tracked, including for equipment costs and human resources for clinical support, technical support, and program management. Standard cost values for a day in-hospital, ED visit, etc. will be used to estimate net cost savings or expenditures. Values for pre- and post-trial health outcome measures (eg, blood test results) will be obtained through hospital clinical records or through the *Medly* database for symptoms. Pre- and follow up questionnaires (baseline, 1-month, and 6-months), will be administered to both control and intervention groups that contain the validated survey tools listed above. Participants will be able to complete the questionnaires at the clinic or complete it at home. Participants that chose to complete the questionnaire at home will be given a pre-paid self-addressed envelope to mail the questionnaire back to the study team. The 1-month questionnaire will be given to participants upon enrolment with instructions to complete the questionnaire one month after starting the trial and to mail it back to the study team using the pre-paid envelope. The study coordinator will call each participant at the 1-month period to remind participants to complete the questionnaire. In addition to the baseline and follow up questionnaires that are applicable to all patient participants (Appendix 3), patients with HF and/or COPD will also receive the validated survey tools listed above (Appendix 4 and 5). Average 7-day blood pressure will also be recorded from patients with a primary diagnosis of hypertension during their first week in the study (baseline) and their last week in the study (6-months). To do this, patients will be provided with a digital blood pressure monitor which they will use to take blood pressure 4 times per day (2 times in the morning and 2 times in the evening) over each 7-day period. Patients will return the blood pressure monitor to the study team who will download the

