**Data Analysis:** Post-trial data and change scores will be compared between the control and intervention groups using independent Student t tests and Mann-Whitney tests (for normally and not normally distributed data, respectively). Paired Student t tests and Wilcoxon signed rank tests will be performed to compare baseline and post-study data within the control and telemonitoring groups. The statistical analyses will be performed using the statistical software application SPSS (IBM Corporation, USA). The cost evaluation will be performed by comparing any savings through reductions in hospitalization, emergency and clinic visits, through the use of the intervention. This will further include amortizing the equipment costs and factoring in additional clinical, technical, and management resources. An analysis of indirect costs will also be performed, such as days absent from work. Interview data will be analyzed using a conventional content analysis approach (49). Two researchers will analyze the transcripts independently and code the transcripts with the software program NVivo (QSR International, Doncaster, Victoria, Australia).

The Principle Investigator will keep all study data in a secure and confidential location for 10 years after the completion of the study and then they will destroyed by shredding of paper or erasing of digital information. All participants will be assigned a unique identifier, which will replace any identifiable information contained in the research data. A list linking the study number with the participants' name will be kept by the Principle Investigator in a secure place in a locked cabinet.

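### Minor: 73 enrolled per group with 15% loss leaves about 62 evaluable, one short of the 63 that the plan requires; power falls by about 0.6 points

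*Combined protocol and SAP*

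**What the plan says.** The sample size paragraph under Patient Recruitment takes a difference of 10.5 points on SF-36 general health and an SD of 21 ("general health dimension of the SF-36 of 10.5 points (39), a score of 57 +/- 21 for the control group"). It concludes: "80% power, and alpha=0.05 (two-sided), the sample size per group was calculated to be 63". It then allows for attrition: "Assuming 15% of patients will be lost to follow-up (including mortality) (36, 37), the sample size per group is 73". The total follows: "Hence 146 patients will be enrolled during the trial and randomized 1:1 into control and telemonitoring groups". The Abstract gives the same total ("we propose a 6-month randomized controlled trial of 146 patients").

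The Data Analysis paragraph, under Outcome Measures, sets the between-group tests: "Post-trial data and change scores will be compared between the control and intervention groups using independent Student t tests and Mann-Whitney tests". The Data Acquisition paragraph shows that baseline scores will be available in both arms: "Pre- and follow up questionnaires (baseline, 1-month, and 6-months), will be administered to both control and intervention groups".

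**The concern.** An allowance for loss should leave the required number of evaluable patients once the assumed fraction has gone. If 15% of those enrolled are lost, the requirement has to be divided by 0.85. The stated 73 is smaller than that division gives, so the enrolment does not quite deliver the 63 per group on which the 80% rests. This paragraph is the plan's only justification of its size, and a reader will take it to mean 80% power after 15% loss. At stake is the accuracy of that statement.

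**Working it through.** **Inputs** (all from the sample size paragraph): difference 10.5; SD 21, so a standardised effect of 10.5/21 = 0.5; two-sided alpha 0.05; power 80%; loss 15%; 73 per group; 146 in total.

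**1. Reproduce the plan's 63.** Normal approximation: n = 2(1.960 + 0.842)² / 0.5² = 62.79, rounded up to 63. This agrees with the plan.

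**2. Apply the plan's loss to the plan's enrolment.**
- Per group: 73 × 0.85 = 62.05, which is 0.95 below 63 and 0.74 below the unrounded 62.79.
- In total: 146 × 0.85 = 124.1 against 126.
- Largest loss that leaves 63: 10/73 = 13.7%. Losing 11 is 11/73 = 15.1% and leaves 62.

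**3. What the inflation would have been.**
- From the unrounded requirement: 62.79/0.85 = 73.87, so 74.
- From the rounded requirement: 63/0.85 = 74.12, so 75.
- Multiplying instead: 63 × 1.15 = 72.45, so 73, which is the stated figure.

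**4. Power at the evaluable numbers** (effect 0.5, two-sided 0.05).

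| Evaluable per group | Normal approximation | t test (noncentral t) |
|---|---|---|
| 62 | 79.5% | 78.9% |
| 63 | 80.1% | 79.5% |
| 64 | 80.7% | 80.1% |

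Going from 63 to 62 costs about 0.6 points on either basis. By the normal approximation, the difference detectable at 80% power, 2.802 × 21 × √(2/n), moves from 10.48 to 10.57 points.

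**5. Scale against chance.** If losses are independent at 15%, the SD of the number retained is √(73 × 0.85 × 0.15) = 3.05 per group. The shortfall of 0.95 is under a third of that. The chance that a given group keeps at least 63 is about 46%.

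**6. Use of the baseline score.** Assume SD 21 at both times, 62 evaluable per group, and a correlation ρ between the baseline and 6-month scores. The documents give neither ρ nor the 6-month SD.
- Adjusted for baseline: effective effect 0.5/√(1 − ρ²), 121 degrees of freedom.
- Change score: effective effect 0.5/√(2(1 − ρ)), 122 degrees of freedom.

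| ρ | Unadjusted 6-month score | Baseline-adjusted | Change score |
|---|---|---|---|
| 0.2 | 78.9% | 80.5% | 58.8% |
| 0.3 | 78.9% | 82.5% | 64.6% |
| 0.5 | 78.9% | 89.0% | 78.9% |
| 0.6 | 78.9% | 93.2% | 87.0% |
| 0.7 | 78.9% | 97.2% | 94.6% |

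Adjustment reaches 80% at ρ of about 0.17, and the change score at about 0.51.

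**The case against.** The strongest reply is that this does not matter. The gap is one patient per group, well inside chance variation in losses, and the 15% is itself a round planning figure. The enrolment target is clear and the same wherever it appears. All of that stands, and it sets the weight of the point. It does not make the sentence correct: the requirement, the loss and the enrolment are all the plan's own figures, and they disagree without any outside assumption.

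A second reply is that no inflation formula is given, so 73 breaks no stated rule. Reading the 15% as a share of completers would give 73. But the sentence applies the percentage to patients, and the natural reading is those enrolled. How 73 was reached remains an inference. The shortfall does not depend on it.

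A third reply concerns the planned t test. On that basis 63 per group gives only 79.5%, and 64 are needed to pass 80%. This stands, so a corrected sentence must not imply that 63 restores 80% on both bases.

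A fourth reply is that Data Analysis already uses the baseline through change scores. This stands in part. A reader might infer that change scores can never make up the lost power, but that is too strong: under the assumptions above they pass 80% once the correlation exceeds about 0.51. Below 0.5 they do worse than the unadjusted score, and adjustment does better at every correlation shown. It is also fair to say that adjustment is an analysis proposal separate from the arithmetic. The arithmetic point stands without it.

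**Conclusion.** The sentence is wrong as written, and the error is minor. At the stated 15% loss, 73 per group yields about 62 evaluable patients. Power is 79.5% (normal approximation) or 78.9% (t test), about 0.6 points below what 63 would give on the same basis. This rests only on the plan's own effect, SD, alpha and loss, with the 15% read as a share of those enrolled.

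A reader might infer that the trial is underpowered in a way that matters, or that enrolment must rise to 148 or 150. The documents do not support that: the deficit is under one expected patient per group, and no design decision turns on it.

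The figures for baseline adjustment are conditional on the assumed correlations and on equal SDs at both times.

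**What to change.** Keep 146 and replace the sentence on loss. Suggested wording: *73 per group leaves about 62 evaluable with 15% loss, giving 79.5% power by the normal approximation or 78.9% by t test; 63 evaluable (80.1% and 79.5% respectively) are kept only if at most 10 of 73 (13.7%) are lost.* This costs one sentence, with no extra patients and no change to conduct.

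Separately, add one line to Data Analysis making the comparison of the 6-month general health score one adjusted for its baseline value, and state the assumed correlation if a power figure is attached to it. The data are already to be collected in both arms, so the only cost is that line.

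### A single block size of 4 within strata lets a recruiter who tracks earlier allocations deduce up to about 30–33% of assignments before consent; withholding the current entry does not prevent this.

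*Combined protocol and SAP*

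**What the plan says.** All of the randomization text is in the Patient Recruitment section.

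- **Ratio and size:** "Hence 146 patients will be enrolled during the trial and randomized 1:1 into control and telemonitoring groups".
- **Blocks:** "The participants will be blocked randomized (blocks of 4) and stratified into groups according to their primary condition". No second block size and no variation are described.
- **Strata:** five conditions ("HF, COPD, hypertension, insulin-requiring diabetes, and CKD"). Two of them are split further. Heart failure is split in two by functional class: "The HF group will further be stratified based on NYHA classification (NYHA class 2-3, NYHA class 4". Hypertension is also split in two: "the hypertensive patients will be stratified to those with and those without diabetes".
- **Source of the sequence:** "the online computer generated randomization tool, Research Randomizer, will be used". The plan does not say who runs the tool, who holds the list, or how an assignment is released.
- **Concealment:** "The study coordinator performing the recruitment will be blinded until the patient has consented to participate".
- **Coordinator's tasks:** the coordinator checks inclusion and exclusion criteria and obtains consent. After that, "the study coordinator will provide the patient and, if appropriate, his/her caregiver with training on the telemonitoring system".

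The Methods section compares usual care with usual care plus telemonitoring on a supplied smartphone and home devices. The term open-label is not used, but neither patient nor staff can be masked to this comparison.

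**The concern.** The concealment sentence protects the next line of the list from being read. It does not protect it from being worked out. A coordinator who recruits both arms and trains the telemonitoring patients knows who went where. The block length is printed in the protocol. Once two patients in a block have gone to one arm, the rest of that block is known without sight of the list.

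The plan leaves some room to act on that knowledge, even without intent:

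- The inclusion criteria require a judgement that the patient can manage the telemonitoring system.
- The coordinator conducts the consent conversation.
- For patients invited by mail, the coordinator telephones non-responders and arranges the meeting date, which affects enrolment order.

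The primary outcome, SF-36, is self-reported. The Data Analysis section compares post-trial values and change scores by t or Mann-Whitney tests and names no baseline covariate. A difference between arms created at recruitment would enter the post-trial comparison unadjusted.

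**Working it through.** The plan gives no figure for predictability, so there is none to reproduce. The total of 146 follows from its own steps: 63 per group, 63 × 1.15 = 72.45, rounded up to 73, and 2 × 73 = 146.

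**Inputs (Patient Recruitment).** 1:1 allocation, N = 146, block size 4. Strata: 5 conditions + 1 extra for the heart failure split + 1 extra for the hypertension split = 7.

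**Step 1: certain assignments in a complete block.** There are 6 equally likely orderings: TTCC, TCTC, TCCT, CTTC, CTCT, CCTT. An assignment is certain when one arm's two places are used up.

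| Position | P(certain) | P(best guess correct) |
|---|---|---|
| 1 | 0 | 1/2 |
| 2 | 0 | 2/3 |
| 3 | 2/6 = 1/3 | 1/3 × 1 + 2/3 × 1/2 = 2/3 |
| 4 | 1 | 1 |
| Sum | 4/3 | 17/6 |
| Per patient (÷ 4) | 33.3% | 17/24 = 70.8% |

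**Step 2: 146 patients in 7 strata.** A last block left incomplete after 1 or 2 patients adds no certain assignment; one left after 3 adds 1/3 on average.

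- Most: only one stratum ends mid-block, with 2 patients over. (146 − 2)/4 = 36 blocks; 36 × 4/3 = 48; 48/146 = 32.9%.
- Fewest: all seven strata end with 2 patients over. (146 − 14)/4 = 33 blocks; 33 × 4/3 = 44; 44/146 = 30.1%.
- Near-equal strata (six of 21, one of 20): 35 blocks; 35 × 4/3 = 46.7; 46.7/146 = 32.0%. Best guess: (35 × 17/6 + 6 × 1/2)/146 = 102.2/146 = 70.0%.

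The Abstract allows insulin-requiring diabetes only as a co-morbidity. With six strata instead of seven the range is about 31% to 33%.

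**Step 3: effect of varying the block size.** Simulation with 21 patients per stratum. The predictor knows the set of sizes and all earlier allocations, and updates by Bayes' rule.

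| Block sizes | Certain | Best guess correct | Predictable at 75% or better |
|---|---|---|---|
| 4 only | 32% | 70% | 32% |
| 4, 6, 8 at random | 2% | 67% | 37% |

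Variation removes nearly all certainty but, if the set of sizes is known, leaves many strong guesses.

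**Step 4: scale on the outcome, by assumption only.** The documents give nothing from which to estimate the bias. Suppose every certain slot (32%) is used, and patients placed in those slots differ between arms by 5 to 10.5 SF-36 points because of selection. The bias is then 0.32 × 5 = 1.6 to 0.32 × 10.5 = 3.4 points. With the plan's SD of 21 and 63 per group, SE = 21 × √(2/63) = 3.74, and the two-sided 5% error rate becomes about 7% to 15%. This is an extreme use of the opportunity, not a forecast.

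**The case against.** **One third is a ceiling.** Reaching it needs one person who sees every allocation in a stratum, keeps a tally and uses the block size. Recruitment runs across several clinics at two hospitals, and the plan does not say that one coordinator covers them all. This stands, and the figure has to be stated with that condition.

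**The coordinator is not the only gatekeeper.** A clinician first determines eligibility, clinic staff verify the mail-out list, and the coordinator who prepares that list is described as outside the care team. Most disease criteria are measurements: ejection fraction, spirometry, eGFR, blood pressure. This also stands and narrows the route to bias. It does not close it: the coordinator has a separate eligibility check, the ability-to-use criterion is a judgement, and consent and timing remain. Clinicians are not fully shielded either, since under Telemonitoring Technology they receive alerts and portal data for monitored patients.

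**Change scores offset part of any baseline imbalance.** True for the change-score comparison. They do not protect the post-trial comparison, or against selection on likely cooperation or course.

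**The plan already withholds the assignment until consent.** It does, and some concealment from the recruiter is implied. But that is no defence against deduction from earlier entries.

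**A reader might multiply 33.3% by 146 and report 49 certain assignments.** That count cannot arise. 146 is not a multiple of 4, and even a single unstratified list gives 48.

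**Conclusion.** The point holds as a weakness in allocation concealment. With one block size of 4, up to 44 to 48 of 146 assignments (30.1% to 32.9%) can be deduced before consent, and the best guess is right about 70% of the time.

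This rests on three conditions: the recruiter knows all earlier allocations in the stratum, knows the block size, and the single stated size means that blocks do not vary. The last is an inference from the text, though a natural one. If coordinators split strata without sharing allocations, the share is lower by an amount the documents do not let us compute.

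A reader might go further and infer that a third of allocations will in fact be known, that patients will be steered, or that the SF-36 difference will be biased by a given amount. The documents support none of these. They do not state the number of coordinators, and they give no basis for the size of any selection effect. What they show is an avoidable opportunity in a trial with unmasked arms and a self-reported primary outcome. I would class the change as a cheap improvement.

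**What to change.** In the randomization paragraph of Patient Recruitment:

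1. Replace the single block size with randomly varying block sizes (4, 6 and 8 would serve). State in the protocol only that sizes vary, and keep the sizes themselves in a document that recruiting staff do not see.
2. Name an existing team member who does not recruit to generate and hold the list.
3. State that this person releases one allocation at a time, after consent is documented.

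Items 2 and 3 and the secrecy of the sizes are essential, because variation alone leaves best-guess accuracy at about 67% for someone who knows the set of sizes.

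Cost: a short text change and a new list before enrolment. The downside is that the largest possible imbalance within a stratum rises from 2 (half of a block of 4) to 4 (half of a block of 8).
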